5.4.2 Trial Suspension Rule

A trial suspension rule will be applicable during the entire trial. This rule is met if a subject vaccinated with CVnCoV experiences an SAE considered related to the trial vaccine by the Investigator or Sponsor.

If this rule is met, enrollment and vaccination with CVnCoV will be suspended within 24 hours after reporting to the trial team. An ad-hoc DSMB meeting will be held to review all safety data per the DSMB charter. Depending on the DSMB assessment of the benefit-risk ratio, including the relationship of the SAE to the trial vaccine, enrollment and vaccination with CVnCoV might be temporarily halted and only be re-started upon approval by the DSMB and competent authority.

5.5 Scientific Rationale for Trial Design

This trial will evaluate the safety, reactogenicity, and immunogenicity of different CVnCoV dose levels in an elderly population (>60 years of age [i.e., 61 years or older]). As the elderly are affected most by SARS-CoV-2, it is critical to investigate CVnCoV in this population and determine an appropriate dose and regimen.

A booster dose will be administered at approximately 2 months (Day 57) or at 6 months (Day 180) after the first dose of the primary regimen to address potentially reduced immunogenicity in the context of immunosenescence in this elderly population. Furthermore, a 0, 1, 6-month schedule is commonly used for licensed vaccines because it allows for an extended period for affinity maturation before the later boost.

The duration of the trial is appropriate for mRNA vaccines, allowing a minimum of 365 days of safety follow-up after the last primary dose for all subjects, to collect and evaluate safety data as needed.

The hepatitis A and pneumococcal vaccines were selected as control because hepatitis A and pneumococcal disease occur in the countries in which the trial is being conducted; subjects will therefore benefit from this control to some degree.

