2 SCHEDULE OF ACTIVITIES

Table 1 Schedule of Trial Assessments and Procedures

Visit Number	Primary Vaccination Period								Booster Vaccination Period								End of Trial		
	1 ^a	2	Phone contact		3	Phone contact	4	Phone contact ^b	5 ^c	Phone contact ^c	6 ^c	Prompt	7	Phone contact ^d	8 ^d	Prompt	Phone contact	9 ^w	
Visit Window (days)	n/a	-0/ +0	-0/ +0	-2/ +4	-2/ +4	-0/ +0	-2/ +4	-2/ +4	-2/ +4	-0/ +0	-2/ +4	-2/ +4	-10/ +10	-0/ +0	-2/ +4	-2/ +4	-0/ +30	-0/ +30	
Trial Day	1	2	7 ^e	15	29	30	43	57	57	58	85	120	180	181	208	270	393	393	
Anchoring	-	1	1	1	1	29	29	29	57	57	57	29	1	180	180	180	180	180	
Signed informed consent	X																		
Inclusion/exclusion criteria	X																		
Demographics	X																		
Medical history	X																		
Vaccination																			
Review of criteria for delay or cancellation of vaccination ^f	X				X				X					X ^g					
Investigational vaccine administration (including 30-minute observation)	X				X				X					X ^g					
Safety Monitoring																			
Physical examination ^h	X ⁱ				X				X					X ^g					
Symptom-directed physical examination ^h		X				X				X						X			
Vital signs ^{h,j}	X	X			X		X		X		X		X		X		X		
ECG	X																		
Diary (re)training ^k	X	X			X		X		X					X ^g					
Diary review ^k		X	X	X	X	X	X	X		X	X				X	X			
Diary reminder ^k		X		X		X	X	X	X	X				X ^g	X				
Solicited AEs ^k	X	X		X	X	X	X	X	X	X	X			X ^g	X	X			
Unsolicited AEs ^k	X	X		X	X	X	X	X	X	X	X	X	X	X	X	X	X	X	X

Visit Number	Primary Vaccination Period								Booster Vaccination Period								End of Trial	
	1 ^a	2	Phone contact		3	Phone contact	4	Phone contact ^b	5 ^c	Phone contact ^c	6 ^c	Prompt	7	Phone contact ^d	8 ^d	Prompt	Phone contact	9 ^w
Visit Window (days)	n/a	-0/ +0	-0/ +0	-2/ +4	-2/ +4	-0/ +0	-2/ +4	-2/ +4	-2/ +4	-0/ +0	-2/ +4	-2/ +4	-10/ +10	-0/ +0	-2/ +4	-2/ +4	-0/ +30	-0/ +30
Trial Day	1	2	7 ^e	15	29	30	43	57	57	58	85	120	180	181	208	270	393	393
Anchoring	-	1	1	1	1	29	29	29	57	57	57	29	1	180	180	180	180	180
SAEs ^l	X	X		X	X	X	X	X	X	X	X	X	X	X	X	X	X	
Intercurrent medical conditions ^l	X	X		X	X	X	X	X	X	X	X	X	X	X	X	X	X	
AEs leading to premature discontinuation ^l	X	X		X	X	X	X	X	X	X	X	X	X	X	X	X	X	
AESIs ^l	X	X		X	X	X	X	X	X	X	X	X	X	X	X	X	X	
Concomitant medication/vaccination	X ^m	X		X	X	X	X	X	X	X	X	X	X	X	X	X	X	
Safety laboratory (~9 mL) ⁿ	X	X			X						X				X			
Safety laboratory in case of abnormal result at previous visit (~9 mL) ⁿ							X		X				X					
Serum pregnancy test (~3 mL) ^o	X																	

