7.7 Therapy Leading to Discontinuation

If a subject requires therapy listed as an exclusion criterion in Section 6.2 (with the exception of a licensed/authorized SARS-CoV-2 vaccine) and which cannot be delayed, discontinuation would be considered to ensure integrity of the trial data, following individual case review, but safety follow-up until 12 months after the last dose of the primary regimen should be pursued.

Licensed/authorized SARS-CoV-2 vaccines are allowed. Receipt of any other investigational SARS-CoV-2 vaccine or vaccines against any other virus from the coronavirus family is prohibited during the trial.

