8.1 Discontinuation of Trial Vaccine Administration

The primary reason for discontinuation of further administrations of trial vaccine doses will be recorded in the subject's eCRF according to the following categories:

- Consent withdrawal by the subject.

The reason for withdrawal, if provided, should be recorded in the eCRF.

Note: All attempts should be made to determine the underlying reason for the withdrawal and, where possible, the primary underlying reason should be recorded (i.e., withdrawal due to an AE should not be recorded in the "voluntary withdrawal" category).

- AE (including known side effects of the trial vaccine).

If discontinuation is due to an AE possibly related to the trial vaccine or trial procedures, the subject must be followed up by additional examinations according to the medical judgment of the Investigator until the condition is resolved or the Investigator deems further observations or examinations to be no longer medically indicated.

- Change in the subject's overall medical status prohibiting further participation.
- Pregnancy (see Section 9.1.2).

Any subject who, despite the requirement for adequate contraception, becomes pregnant during the trial will not receive further trial vaccine doses. The site should maintain contact with the pregnant subject and complete a "Clinical Trial Pregnancy Form" as soon as possible. In addition, the subject should be followed up until the birth of the child, or spontaneous or voluntary termination. When pregnancy outcome information becomes available, the information should be captured using the same form. The subject should be reported as an IMP discontinuation and the reason (i.e., pregnancy) should be given.

- Virologically-confirmed SARS-CoV-2 infection (as specified in Section 9.3).
- Trial terminated by the Sponsor (in which case the minimum safety follow-up of 1 year after the last trial vaccine dose would be performed).

- Major protocol deviation.
- Other.

Note: The specific reasons should be recorded in the “specify” field of the eCRF.

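### Table 1 lets a fully compliant subject finish 350 days after dose 2, so the 365-day minimum safety follow-up in protocol section 5.5 is not guaranteed

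*Protocol*

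**What the plan says.** Protocol section 5.5 presents the trial duration as "allowing a minimum of 365 days of safety follow-up after the last primary dose for all subjects". It is worded as a minimum, it covers every subject, and the clock starts at the second primary dose.

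The timing comes from Table 1 in protocol section 2. The scheduled days read "Trial Day 1 2 7 ^e 15 29 30 43 57 57 58 85 120 180 181 208 270 393 393", and the row that says what each contact is timed from reads "Anchoring - 1 1 1 1 29 29 29 57 57 57 29 1 180 180 180 180 180". Lined up column by column with the window row:

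- Dose 2: Day 29, window -2/+4, timed from Day 1.
- Visit 7: Day 180, window -10/+10, timed from Day 1.
- Final phone contact and Visit 9: Day 393, window -0/+30, both timed from Day 180.

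Section 6.3 directs that a delayed vaccination stay within the Table 1 windows, so dose 2 on Day 33 complies.

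Two other sections mention a year of follow-up. Section 7.7 covers subjects who need an excluded therapy and for whom discontinuation is considered: "safety follow-up until 12 months after the last dose of the primary regimen should be pursued". Section 8.1, under the reason that the sponsor ends the trial, says that "the minimum safety follow-up of 1 year after the last trial vaccine dose would be performed".

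**The concern.** A guaranteed interval after dose 2 needs the end of follow-up to be tied to dose 2. Table 1 ties it to Visit 7, which is itself tied to dose 1 and may be ten days early. The -0 on the final contact looks like a floor, but it is a floor relative to a visit that can move forward while dose 2 moves back.

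The occurrence of SAEs and AESIs throughout the trial is a primary endpoint (protocol section 4.2.1), and section 5.5 rests the trial's length on this figure. A report that repeats the claim of at least 365 days in all subjects could be untrue for subjects who kept to every window.

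**Working it through.** **Inputs (protocol Table 1)**

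- Actual day of dose 2, D2: 29 - 2 = 27 to 29 + 4 = 33.
- Actual day of Visit 7, V7: 180 - 10 = 170 to 180 + 10 = 190.
- Offset from Visit 7 to the final contact: 393 - 180 = 213 days, plus w = 0 to 30 days.

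**Formula**

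Follow-up after dose 2 = (V7 + 213 + w) - D2, in elapsed days. Add 1 if the dose day is counted.

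**The plan's own figure.** On the nominal schedule, (180 + 213 + 0) - 29 = 364 elapsed days, or 365 counting the dose day. The stated 365 is thus reproduced on nominal days under inclusive counting.

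**What the windows allow**

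| Case | Calculation | Elapsed days | Counting the dose day |
|---|---|---|---|
| Nominal | 180 + 213 - 29 | 364 | 365 |
| Dose 2 on Day 33, Visit 7 on time | 180 + 213 - 33 | 360 | 361 |
| Dose 2 on time, Visit 7 on Day 170 | 170 + 213 - 29 | 354 | 355 |
| Both (minimum) | 170 + 213 - 33 | 350 | 351 |
| Maximum | 190 + 213 + 30 - 27 | 406 | 407 |

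**How much of the window is affected.** There are 7 permitted days for dose 2 and 21 for Visit 7, so 7 x 21 = 147 combinations. With the final contact on its first permitted day (w = 0), follow-up is below 365 elapsed days when V7 - D2 < 152, which is 84 of the 147. With inclusive counting the condition is V7 - D2 < 151, which is 77 of the 147. These count combinations of days, not subjects; the documents give no distribution of actual visit dates.

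**Sensitivity to the anchor.** If Day 393 were timed from Day 1, the minimum would be 393 - 33 = 360. If it were timed from actual dose 2 with today's spacing, the minimum would be 393 - 29 = 364.

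**Booster recipients, a separate point.** After a Day 180 booster, planned follow-up is 393 - 180 = 213 days, up to 213 + 30 = 243. After a Day 57 booster it is nominally 393 - 57 = 336 days. One year after a Day 180 booster would be trial day 180 + 365 = 545.

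**The case against.** **The +30-day window lets everyone reach 365 days.** In the worst case, dose 2 plus 365 days is Day 33 + 365 = 398, inside the permitted Days 383 to 413. Section 5.5 also speaks only of allowing this follow-up. This is correct, but a window that permits 365 days does not require them, and a minimum is set by the lower edge.

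**The 350 figure needs three extremes in one subject:** a late dose 2, an early Visit 7, and a final contact on its first permitted day. This stands as a remark on frequency. It does not restore the minimum, since a late dose 2 or an early Visit 7 alone is enough when the final contact is on its first permitted day.

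**It is a matter of counting.** For the nominal 364 this is right, and that figure is not a defect in itself. The minimum is 351 under inclusive counting, so the shortfall remains.

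**The anchoring row was read from a PDF, and it lists the Day 57 visit as its own anchor.** That is a reason for caution, but an anchor on Day 1 still gives only 360.

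**Little depends on it.** The trial is descriptive, the endpoint runs to the end of the trial and not to a fixed day, and the largest gap is 15 of 365 days (about 4%). This stands and limits the weight of the point.

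**A stronger reading that the documents do not support.** A reader might set section 8.1's year after the last trial dose against the 213 days that follow a Day 180 booster and conclude that the plan breaks its own minimum for the 60 subjects due that booster. But section 8.1 attaches the year to sponsor termination only, and section 5.5 counts from the last primary dose. A booster recipient has the same follow-up after dose 2 as anyone else, so no general minimum is breached. What remains is a smaller inconsistency. Section 8.1 refers to a minimum after the last trial dose that is defined nowhere else. Read literally, a Day 180 booster recipient would be followed to about Day 545 if the sponsor ends the trial, but nominally only to Days 393 to 423 if it completes. Day 57 booster recipients are in a similar position.

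**Conclusion.** The minimum in section 5.5 is a property that the schedule does not have. The windows guarantee 350 elapsed days after dose 2 (351 inclusive), a shortfall of up to 365 - 350 = 15 days in a fully compliant subject. This assumes that Table 1's windows and anchors are as printed and that the final contact may take place on its first permitted day.

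The consequence is a factual claim that may be wrong in the report. It does not bias any planned analysis. SAP section 10.8, which censors safety endpoints from the day after unblinding, can shorten the analysed follow-up further, but this finding does not rest on it.

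The differing reference doses in sections 5.5 and 8.1 are a minor inconsistency to be reconciled. Which length of follow-up is clinically appropriate is not judged here.

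**What to change.** Reconcile section 5.5 with Table 1 in one of two ways:

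1. Restate the section 5.5 figure as what the windows deliver: at least 350 days after the last primary dose.
2. Keep 365 days and tie the earliest permitted final contact to the actual date of dose 2, with an offset of 365 days. This must cover both Day 393 columns, the phone contact and Visit 9. Changing the anchor while keeping today's spacing would give only 364 elapsed days.

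In either case, report actual follow-up from dose 2 by group, including the minimum and the number of subjects below 365 days. SAP sections 12.1 and 12.5 list no such summary now.

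Section 7.7 should stay as it is. It is an instruction for individual subjects, not a description of Table 1, and need not be cut to match the windows.

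As a minor item, state in sections 5.5 and 8.1 which dose each follow-up period is counted from, and whether section 8.1 is meant to ask for longer follow-up of booster recipients after termination than after completion.

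Cost: the first option changes one figure. The second changes the entries for two columns and defers a final contact by at most 15 days, which fits inside the existing 30-day window. The follow-up summary uses dates that the trial already records.

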5.6 Justification for Dose

Two provisional CVnCoV dose levels (6 and 12 µg) will be evaluated. Based on favorable immunogenicity data and tolerable safety/reactogenicity data administered with 12 µg in Trial CV-NCOV-001, the DSMB endorsed the decision to implement the 12 µg dose in this phase 2a trial. Refer to the Investigator's Brochure for an overview of the CVnCoV non-clinical data.

Additional higher, lower, and/or intermediate dose levels might be evaluated depending on the outcomes of Trial CV-NCOV-001, as well as data from Trial CV-NCOV-002. Identification of immunogenic dose levels with lower mRNA content might be of particular importance for efficient vaccination in a worldwide viral outbreak setting.

5.7 End of Trial Definition

A subject is considered to have completed the trial when he/she has completed all visits applicable for the group to which he/she was randomized/assigned to at trial entry.

End of Trial is defined as the point at which the last subject has completed the last visit or last phone contact.

6 TRIAL POPULATION

The criteria for enrollment are to be followed explicitly. If it is noted that a subject who does not meet 1 or more of the inclusion criteria and/or meets 1 or more of the exclusion criteria is inadvertently enrolled and dosed, the Sponsor must be contacted immediately.

6.1 Inclusion Criteria

Subjects will be enrolled in this trial only if they meet **all** of the following criteria:

1. Healthy male and female subjects ≥ 18 years of age.

A healthy subject is defined as an individual who is in good general health, according to the Investigator's assessment. Chronic health conditions are acceptable if the condition is considered well controlled with treatment according to the discretion of the Investigator.
2. Expected to be compliant with protocol procedures and available for clinical follow-up through the last planned visit.
3. Subjects who are able to understand and willing to provide informed consent.
4. Physical examination without clinically significant findings according to the Investigator's assessment.
5. Body mass index (BMI) ≥ 18.0 and ≤ 32.0 kg/m².
6. Female subjects of childbearing potential: at the time of enrollment, negative human chorionic gonadotropin (hCG) pregnancy test (serum) for female subjects presumed to be of childbearing potential on the day of enrollment. On Day 1 (pre-vaccination): negative urine pregnancy test (required if serum pregnancy test was performed more than 3 days before).
7. Female subjects of childbearing potential must use highly effective methods of birth control from 2 weeks before the first administration of the trial vaccine until 3 months following the last administration. The following methods of birth control are considered highly effective when used consistently and correctly:
 - Combined (estrogen and progestogen containing) hormonal contraception associated with inhibition of ovulation (oral, intravaginal or transdermal);
 - Progestogen-only hormonal contraception associated with inhibition of ovulation (oral, injectable or implantable);
 - Intrauterine devices;
 - Intrauterine hormone-releasing systems;
 - Bilateral tubal occlusion;
 - Vasectomized partner;
 - Sexual abstinence (periodic abstinence [e.g., calendar, ovulation, symptothermal and post-ovulation methods] and withdrawal are not acceptable).

Male subjects should be instructed not to get their partners pregnant until 3 months after the last administration.

Refer to the Clinical Trial Facilitation Group recommendations on contraception and pregnancy testing for further details [32].

6.2 Exclusion Criteria

Subjects will not be enrolled in this trial if they meet **any** of the exclusion criteria.

1. Use of any investigational or non-registered product (vaccine or drug) other than the trial vaccine within 28 days preceding the administration of the trial vaccine, or planned use during the trial period.
2. Receipt of any other vaccines within 28 days prior to enrollment in this trial or planned receipt of any vaccine within 28 days of trial vaccine administration (primary dose or booster dose).
3. Receipt of any investigational or licensed/authorized SARS-CoV-2 or other coronavirus vaccine prior to the administration of the trial vaccine.
4. Any treatment with immunosuppressants or other immune-modifying drugs (including, but not limited to, corticosteroids, biologicals, and methotrexate) within 6 months prior to the administration of the trial vaccine or planned use during the trial, with the exception of topically-applied, inhaled, or intranasal steroids.
5. Use of hormonal therapy for gender reassignment.
6. Any medically diagnosed or suspected immunosuppressive or immunodeficient condition based on medical history and physical examination, including known human immunodeficiency virus infection, hepatitis B virus infection, and hepatitis C virus infection.
7. History of immune-mediated or autoimmune disease.
8. History of angioedema (known C1 inhibitor deficiency).
9. History of anaphylaxis or allergy to any component of CVnCoV or aminoglycoside antibiotics.
10. History of or current alcohol and/or drug abuse.
11. Subjects who are active smokers, were active smokers within the last year (including any vaping in the last year), or have a total smoking history ≥ 10 pack years. A pack year is calculated by multiplying the number of packs of cigarettes smoked per day by the number of years the person has smoked.
12. History of virologically-confirmed SARS, MERS, or COVID-19 disease or known exposure (without any personal protective equipment) to an individual with confirmed COVID-19 disease or SARS-CoV-2 infection within the past 2 weeks.
13. Administration of immunoglobulins and/or any blood products within the 3 months preceding the administration of any dose of the trial vaccine.

14. Presence or evidence of significant uncontrolled acute or chronic medical or psychiatric illness. Significant medical or psychiatric illnesses include but are not limited to:
 - Uncontrolled respiratory disease (e.g., chronic obstructive pulmonary disease, asthma), including use of the following asthma medications: intravenous corticosteroids, leukotriene modifiers, biologics.
 - Uncontrolled cardiovascular disease (e.g., congestive heart failure, cardiomyopathy, ischemic heart disease, history of stroke, peripheral artery disease, pulmonary embolism).
 - History of myocarditis or pericarditis as an adult.
 - Diabetes mellitus (insulin-dependent).
 - Uncontrolled neurological disorders or Guillain-Barré syndrome or history of seizure, except for febrile seizures during childhood.
 - Current or past malignancy, unless completely resolved without sequelae for >5 years.
15. Foreseeable non-compliance with protocol, as judged by the Investigator.
16. For female subjects: pregnancy or lactation.
17. Subjects with impaired coagulation or any bleeding disorder in whom an intramuscular injection or a blood draw is contraindicated. This includes subjects on treatment with anticoagulants (e.g., vitamin K antagonists, novel oral anticoagulants, and heparin). Use of platelet aggregation inhibitors is not exclusionary.
18. Subjects employed by the Sponsor, Investigator, or trial site, or relatives of research staff working on this trial.
19. Subjects considered at the Investigator's discretion to be at increased risk of exposure to COVID-19 disease.

6.3 Vaccine Delay Recommendations

After enrollment, subjects may encounter clinical circumstances that warrant a delay of trial vaccine administration. These situations are listed below:

- Subjects with a clinically significant (Grade ≥ 2) active infection or other acute disease (as assessed by the Investigator) or temperature $>38.0^{\circ}\text{C}$ ($>100.4^{\circ}\text{F}$), within 3 days of intended trial vaccination. Further dose administration should be delayed until the active infection or other acute disease has recovered to Grade ≤ 1 or the subject's temperature has decreased to $\leq 38.0^{\circ}\text{C}$ ($\leq 100.4^{\circ}\text{F}$) for at least 3 days, if this still allows to vaccinate the subject as per the predefined interval. Temperature should be measured orally.
- Subjects who took antipyretic medication within 8 hours before intended trial vaccination.

In case of delay, the vaccination should take place within the allowed time windows specified in Table 1.

6.4 Failure to Meet Eligibility Criteria

The Investigator must account for all subjects who sign an informed consent form (ICF). If the subject is found to be not eligible (i.e., did not meet all inclusion criteria or met one or more exclusion criteria), the Investigator should document this in the subject's source data and electronic case report form (eCRF).

Re-doing the full assessments for eligibility assessment as per Table 1 or re-testing (i.e., re-doing a single assessment) is allowed if the reason for ineligibility is a transient event.

An example of a condition under which re-assessment may be considered includes:

- Subjects who required treatment for an acute illness that resolved (e.g., a urinary tract infection) may be re-assessed once the illness resolved or the medical problem stabilized.

An example of a condition under which re-testing may be considered includes:

- Subjects who have clinical laboratory test value(s) that are not in line with the medical history and clinical evaluation of the subjects may be re-tested to confirm the value of the tests, if still allowed within the enrollment period (Day -21 to Day 1). If not feasible, the subject should be re-assessed for eligibility.

